1.2.1.4. Toxicology

No effects were observed in a single-dose safety pharmacology neurobehavioral study in the rat up to the highest tested dose of 150 mg/kg, which was considered the NOEL. In a respiratory study in the rat, an increase of the respiratory rate and minute volume without affecting the tidal volume was observed. The NOEL for respiratory effects was therefore 100 mg/kg. No inhibition of the I_{Kr} channels was observed at concentrations up to 1 mM and no meaningful changes were seen in terms of blood pressure,

body temperature, heart rate or ECG intervals following oral doses up to 75 mg/kg in conscious Beagle dogs, while the highest dose of 125 mg/kg produced transient increase in heart rate and body temperature along with lower systolic-, mean arterial-, pulse pressure as well as shorter PR, RR, and QT. The dose of 75 mg/kg was the NOEL for cardiovascular function in the dog.

Oral gavage toxicology studies have been conducted with DF2755A for up to 4 weeks duration with 2 week recovery periods in rats and dogs. Range-finding studies of 7 days duration were performed in rats and dogs at dose levels of up to 800 and 900 mg/kg/day, respectively. Findings in rats and dogs were similar; in the rat, at the dose of 800 mg/kg/day, subdued behaviour, piloerection, bradypnoea and rales were observed along with decreased food intake. Microscopic effects included mixed cell infiltration and oedema of the glandular mucosa of the stomach, periportal inflammation in the liver and degenerative changes in the proximal tubules, mainly at the higher dose level. Biochemistry findings included increases in transaminases, lipids and inorganic phosphorus while haematology findings included increased platelet count, mean corpuscular volume and relative reticulocyte counts. Notable findings in dogs at the 900 mg/kg/day dose level included sporadic instances of haemorrhage (discoloured ears and eyes; dark or red faeces), vomiting, diarrhoea, tremors and lethargy. Food intake and body weight were also reduced. Microscopic findings at the higher dose included oedema, congestion and inflammatory infiltration and degeneration of the fundus mucosa, duodenum and ileum. In the liver, diffuse or centrilobular hepatocellular hypertrophy, single cell necrosis or minimal focal necrosis and diffuse hepatocellular vacuolation and periportal inflammation were observed. In the kidneys, tubular degeneration and regeneration and tubular dilation were observed. Biochemical findings included increased transaminases, total bilirubin, urea, creatinine and cholesterol and decreased electrolytes, glucose, total protein and albumin. Haematology findings included WBC parameter alterations and decreased platelet counts and decrease of the prothrombin time.

In the 28-day repeated dose studies in rats and dogs, toxicity findings were consistent with those observed in the range-finding studies. In the rat, DF2755A was administered at dose levels of 60 to 300 mg/kg/day (BID). No mortality occurred during the study and no treatment-related effects were noted in terms of food consumption, ophthalmoscopy or urine parameters. At 300 mg/kg/day, hunched posture and slight salivation were seen together with a lower body weight gain. The same dose level produced slight increases in transaminases. Decreased total protein, total globulin and glucose were seen along with increased lipids. Increased inorganic phosphorus and decreased potassium and calcium were also seen, while decreased urea and creatinine concentrations were observed in females. At histopathology, mixed cell infiltration, oedema, haemorrhage and erosions were noted in the GI tract but showed no dose-dependency and were seen also in control animals. Changes reminiscent of metabolic adaption were seen in the liver and kidneys correlated with increased organ weight and were fully reversible at recovery. Slight atrophy of the thymus, diffuse hypertrophy of the adrenal cortex and reduced secretion in the prostate, coagulating gland and seminal vesicles were also seen at 300 mg/kg/day. Other findings at 300 mg/kg/day included increased incidence of splanchnic haematopoiesis and increased bone marrow cellularity, correlating with decreased RBC count, haemoglobin, haematocrit and mean corpuscular haemoglobin and increased relative reticulocytes; all these changes were reversible at recovery. Slight increases in WBCs correlated with the inflammatory changes seen in the stomach. In the dog, repeated administration of DF2755A at dose levels in the range 40 to 200 mg/kg/day was generally well tolerated and no effects on body weight, food consumption, ophthalmoscopy, ECG examination or clinical pathology parameters were seen at any dose. Macroscopic findings included discolouration of the ileocaecal valve and reddish foci in the colon, rectum and pylorus. Upon microscopic examination, haemorrhage or congestion in the ileocaecal valve and/or colon as well as haemorrhage, erosion, mixed cell infiltration, and congestion of the pylorus were observed. Centrilobular hepatocellular hypertrophy was observed in females at mid and high dose and correlated with increased liver weights, but was not associated with any degenerative or inflammatory changes. In both species, the GI effects are similar to effects seen with other propionic acid derivative and likely a class effect, while the liver and kidney changes are considered to represent an adaptive metabolic phenomenon and of limited toxicological concern. The dose of 120 mg/kg/day was considered to be the NOAEL for repeated 4-week oral administration in the rat, while the NOAEL in the dog was 40 mg/kg/day.

Electron microscopy investigation in the liver of rats indicated the presence in the hepatocytes of areas of low electron-density and homogeneous appearance interspersed among the mitochondria and

rough endoplasmatic reticulum. However, no indication of cellular or organelles alterations were observed.

The *in vitro* genetic toxicity test for bacterial mutations (Ames assay) and chromosomal aberrations in human lymphocytes revealed no genotoxic potential for DF2755A. No evidence of clastogenicity or aneugenicity was found in the rat micronucleus test following administration of DF2755A by oral gavage up to the maximum tolerated dose level of 300 mg/kg/day.

A male and female fertility study combined with embryo-fetal development study with DF2755A Monohydrate was done in rats by oral gavage. Ninety-six male and ninety-six main female Wistar Han rats were assigned to four dose groups. The test item was administered once daily by oral gavage at doses of 50, 100 and 150 mg/kg (Groups 2, 3 and 4 respectively). The rats of the control group received the vehicle, water, alone. In addition, five satellite animals (females only) per treatment group and three satellite females in the control group were exposed and used for toxicokinetic blood sampling on Day 17 post-coitum. Males were exposed for 43-46 days, i.e. 2 weeks prior to mating, during mating, and up to termination. Mated females were exposed for 33-46 days, i.e. during 2 weeks prior to mating, during mating, and continuing until Day 17 post-coitum, inclusively. Females without evidence of mating were dosed until one day prior to euthanasia.

No reproduction and developmental toxicity was observed up to a dose level of 150 mg/kg. A slight, treatment related decrease in body weight gain was observed in males treated at 150 mg/kg from Day 4 of treatment onwards, resulting in approximately 5% lower absolute body weights at the end of treatment. As this effect was very small and no concurrent effect on food consumption was noted, this was considered not to be adverse.

No maternal toxicity was observed in females at any dose groups.

In conclusion the NOAEL to be considered for the calculation of the maximum recommended starting dose (MRSD) in humans are:

TOX 4 week (28 day) and corresponding exposure levels

RAT:	NOAEL 120 mg/kg (60 mg/kg b.id.)	C _{max_{ss}}	193 µg/mL	AUC _{ss(0-24)}	2275 h*µg/mL
DOG:	NOAEL 40 mg/kg (20 mg/kg b.id.)	C _{max_{ss}}	18.00 µg/mL	AUC _{ss(0-24)}	81.75 h*µg/mL

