Quantitative whole body autoradiography (QWBA) studies show that [¹⁴C]DF2755A is fairly rapid distributed into tissues when administered orally to both albino and partially pigmented male rats and widespread in the body, and no melanin binding is observed by the compound and/or its metabolites. The maximum concentrations of radioactivity in the vast majority of tissues were achieved at 2h and the largest proportion of dose was recovered in CCI [REDACTED] and CCI [REDACTED] at 24h. Very low concentration were found CCI [REDACTED] ranging from 0.996 1.79 µg/eq DF2755A/g of tissue after 2h of administration in albino and partially pigmented rats. Indicating that the compound do not CCI [REDACTED] ratio were 0.03 in abino rats and 0.04 in partially pigmented rats).

Maternal tissue distribution of the radiolabelled compound [¹⁴C]DF2755A into pregnant female rats is comparable with tissue distribution of not radiolabelled compound DF2755A in male and female rats. The maximum concentrations of radioactivity were visible in foetal tissues at 6h after the administration and excreted also into milk, meaning that pups would be exposed to the compound.

The toxicokinetic of DF2755A has been studied after repeated administration (28 days) of DF2755A in rat at the dose of 30, 60 and 150 mg/kg b.i.d. corresponding to 60, 120 and 300 mg/kg/day.

The plasma concentration time curves displayed a clear double peak pattern associated with the twice daily dosing of DF2755A (figure 5). The plasma concentrations of DF2755A increased rapidly after the first and second dosing. The peak plasma concentration was determined after the first and the second administration. After the first dosing the peak plasma concentration was reached 1 or 2h after dosing, after the second dosing the peak plasma concentration was reached 4h after dosing, i.e. 12h. For all

groups t_{last} was 24h, as this was the time point on which the last blood sample was taken. No consistent changes in t_{max} in time, dose or sex were observed.

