Time-dependent change in exposure was evaluated by comparing the C_{max} values after the first and second administration and the AUC values in time. In general no clear differences were noted between the C_{max} values after the first and second administration in time. At all dose levels AUC_{0-8} , AUC_{8-24} , and AUC_{last} values were comparable on Day1 and Week4 in both male and female animals, indicating no accumulation or induction occurred at the dose levels used in this study (Table 5).

[figure not shown]

Figure 5: Mean plasma concentration-time profiles of DF2755A in Day 1 and Week4- after 30, 60 and 150 b.i.d. in male and female.

Table 5: Toxicokinetic parameters in plasma following a single and multiple oral administration in rats at different doses

PK Parameters	Group2 30mg/kg - b i.d.		Group3 60mg/kg b i.d.		Group4 150mg/kg - b i.d.	
	Male	Female	Male	Female	Male	Female
Day 1						
t_{last} (h)	24	24	24	24	24	24
$t_{max,1}$ (h)	2	1	1	1	2	1
$t_{max,2}$ (h)	12	12	12	12	12	12
$C_{max,1}$ (μg/mL)	53.5	101	145	171	306	325
$C_{max,2}$ (μg/mL)	76.3	99.4	178	193	291	325
AUC_{0-8} (μg·mL/h)	321	507	928	935	1750	1890
AUC_{8-24} (μg·mL/h)	759	1060	2100	2210	3860	3980

PK Parameters	Group2 30mg/kg - b.i.d.		Group3 60mg/kg b.i.d.		Group4 150mg/kg - b.i.d.	
	Male	Female	Male	Female	Male	Female
AUC _{last} (μg·mL/h)	1080	1560	3030	3150	5600	5870
#AUC _{last} (μg·mL/h)	18.0	26.1	25.3	26.2	18.7	19.6
AUC _∞ (μg·mL/h)	1210	1930	4130	4560*	8680	9000
#AUC _∞ (h·kg·μg·mL/mg)	20.2	32.2	34.5	38.0	28.9	30.0
t _{1/2}	5.70	9.64	9.29	13.0	11.3	13.5
Vz/F	407	432	389	492	565	649
Week4						
t _{last} (h)	24	24	24	24	24	24
t _{max,1} (h)	1	1	1	1	1	2
t _{max,2} (h)	12	12	12	12	12	12
C _{max,1} (μg/mL)	71.5	137	180	210	353	375
C _{max,2} (μg/mL)	72.3	100	164	222	311	347
AUC ₀₋₈ (μg·mL/h)	426	679	1040	1200	2150	2290
AUC ₈₋₂₄ (μg·mL/h)	798	1120	1960	2590	4060	4400
AUC _{last} (μg·mL/h)	1220	1800	3000	3790	6210	6680
#AUC _{last} (μg·mL/h)	20.4	30.0	25.0	31.6	20.7	22.3
t _{1/2} (h)	7.53	7.16	9.67	9.25	19.9	9.26

t_{max,1}, t_{max,2}, C_{max,1} and C_{max,2}, are the t_{max} and C_{max} (peak concentration) after respectively the first and second dosing
:dose-normalized to 1mg/kg; *:approximation

The toxicokinetic of DF2755A has been also studied after repeated administration (28 days) of DF2755A in dogs at the dose of 20, 50 and 100 mg/kg b.i.d. (corresponding to 40, 100 and 200 mg/kg/day)

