Blood was sampled for toxicokinetic evaluation on Day1 and in Week 4. Evaluation of the toxicokinetic behavior of DF2755A resulted in the following observations: The plasma concentration time curves display a clear double peak pattern associated with the twice daily dosing of DF2755A (Figure 6).

The peak plasma concentration was determined after the first and the second administration, and was reached 1 or 2h after dosing. For all groups t_{last} was 24h. Generally, exposure increased in a dose proportional manner over the dose range. Exposure to DF2755A did not change importantly upon repeated dosing and no gender differences in exposure were observed during the study.

Table 6: Toxicokinetic parameters in plasma following a single and multiple oral administration in dogs at different doses

PK parameters	DF2755A					
	M	F	M	F	M	F
DOG						
DAY1						
DOSE BID(mg/kg)						
20			50		100	
Tmax (h) ¹	1	1	1-2 ⁵	1-2 ⁵	1	1
Tmax (h) ²	9-10 ⁵	9-10 ⁵	9-10 ⁵	9	9-10 ⁵	9
Cmax (μg/mL) ¹	17.1	29.0	77.9	43.3	168	128
Cmax (μg/mL) ²	21.9	22.8	36.7	73.3	123	160
AUC ₀₋₈ (μg·mL/h)	45.2	55.5	174	115	366	291
AUC ₈₋₂₄ (μg·mL/h)	80.9	109	328	357	712	779
AUC _{last} (μg·mL/h)	126	165	501	471	1080	1070
AUC _{inf} (μg·mL/h)	128 [*]	167 [*]	515 [*]	539 [*]	1090 [*]	1080 [*]
T _{1/2} (h)	1.92	2.66	2.38 [*]	2.57 [*]	1.62 [*]	1.94 [*]
V _{ss} (L/kg)	968	961	696	732	443	600
WEEK 4						
Tmax (h) ¹	1	1-2 ⁵	1-2 ⁵	1-2 ⁵	1	1-4 ⁵
Tmax (h) ²	9	9	9-10 ⁵	9	9-10 ⁵	9-10 ⁵
Cmax (μg/mL) ¹	18.8	17.4	48.1	58.8	120	130
Cmax (μg/mL) ²	19.2	16.7	37.9	34.3	100	86.6
AUC ₀₋₈ (μg·mL/h)	41.0	50.1	132	145	268	279
AUC ₈₋₂₄ (μg·mL/h)	77.2	86.3	308	255	554	599
AUC _{last} (μg·mL/h)	118	136	440	399	822	878

PK parameters		DF2755A					
DOG		M	F	M	F	M	F
T _{1/2(h)}		2.65	4.04 [*]	2.22	6.30 [*]	2.11 [*]	2.40 [*]

^{*}approximation; \$:range ,tmax¹,tmax²,Cmax¹,Cmax², are the tmax and Cmax (peak concentration)after respectively the first and second dosing

[figure not shown]

Figure 6: Mean plasma concentration-time profiles of DF2755A in Day 1 and Week4- after 20, 50 and 100 b.i.d. in male and female in dogs.

DF2755A showed moderate permeability in Caco-2 and MDCK cells without evidence for active efflux.

In vitro protein binding studies show that DF2755A is highly bound to plasma proteins in rat, dog and human species.

Table 7 DF2755A protein binding to plasma proteins in rat, dog and human.

DF2755A tested concentration (expressed as DF2755Y)	% Protein binding in plasma		
	Rat	Dog	Human

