3.3.3.2. Dose Escalation

The dose escalation is designed to progress from the first to the highest dose up to the occurrence of relevant events supporting Maximal Tolerated Dose (MTD) determination.

At the end of each dose level, an interim safety report will be issued by the Investigator. A dose escalation teleconference meeting will be held between the Investigator and the Sponsor representatives, and the decision on how to proceed (e.g. next higher dose) will be taken on the basis of a blind safety and pharmacokinetic data review.

The following safety parameters will be reviewed for both part, for all the subjects:

- Any adverse events reported;
- All laboratory parameters outside of ranges;

- Concomitant therapy;
- Physical examination abnormalities;
- Vital signs abnormalities;
- ECG abnormalities.

For dose escalation, Pharmacokinetic data on plasma (quantitative determination of DF2755A bound and unbound; qualitative and preliminary quantitative determination of known metabolites), urine and faeces recovery (qualitative and quantitative determination of parent compound and qualitative and preliminary quantitative investigation of known metabolites) will be considered by using, for each new dose level, the pharmacokinetic results of the previous dose level in order to re-estimate the safety margin based on the animal-human exposure ratio. This re-estimation must be taken into account when deciding whether to proceed to the next dose level.

The exposure does not exceed the AUC of 1000 $\mu\text{g}\cdot\text{h}/\text{mL}$.

Identification of non-acceptable risks or significant proportion of AEs with common pathological pattern can justify the modification of the dose escalation design.

After mutual agreement between the Sponsor and the Investigator and if it is considered useful for the selection of the next dose level, the treatment of a specific subject and/or a cohort may be unblinded before the next dose level of DF 2755A is administered.

At the end of the teleconference meeting, the following decisions can be taken:

- Dose escalation will continue as scheduled;
- An intermediate dose between the current dose and the following dose will be administered to the next cohort;
- A lower intermediate dose, between the current dose and the dose administered in the previous cohort will be administered to the next cohort;
- The current dose will be repeated in the next cohort;
- The study will be stopped.

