3.5.4. Stopping rule for dose escalation

The safety review committee will decide to stop the dose escalation as planned per protocol in case of occurrence of:

- 2 subjects experiencing severe non serious AEs of the same organ class and nature related to the study drug,
- 4 subjects (for SAD) and 8 subjects (for MAD) experiencing study drug related moderate non serious AEs (that are considered directly related to the drug effect unless they resolved despite the continuation of the treatment),
- 2 subjects of the group experience a significant increase (i.e. $> 3 N$) ALAT,
- 2 subjects of the group experience simultaneous increases of total bilirubin ($> 2 N$), ALAT ($> 2 N$) and alkaline phosphatases ($> 1.5 N$),

- 2 subjects has a sustained QTc value > 500 ms (confirmed by a second ECG under strict resting position),
- One subject presents a C_{max} or $AUC_{(0-24h)}$ values respectively above 150 $\mu\text{g}/\text{mL}$ and 1000 $\mu\text{g}/\text{mL} \cdot \text{h}$,
- The mean C_{max} and $AUC_{(0-24h)}$ leads to believe taking into account the dose increase that C_{max} or $AUC_{(0-24h)}$ values of 125 $\mu\text{g}/\text{mL}$ and 600 $\mu\text{g}/\text{mL} \cdot \text{h}$ will be overpass with the following planned higher dose,
- In MAD part the mean at the steady state C_{max} and $AUC_{(t)}$ leads to believe taking into account the dose increase that C_{max} or $AUC_{(0-24h)}$ values of 125 $\mu\text{g}/\text{mL}$ and 800 $\mu\text{g}/\text{mL} \cdot \text{h}$ will be overpass with the following planned higher dose,

In one of the cases listed above, the dose group in progress will be stopped and the blind could be broken. Regarding laboratory and QTc abnormalities described above, if unblinding confirms that at least two subjects presenting these abnormalities were receiving the active drug the dose escalation will be stopped.

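### Protocol 1.2.1.4: the NOAEL exposures labelled AUCss(0-24), 2275 (rat) and 81.75 (dog) h*µg/mL, are 16-hour AUC8-24 means; the 0-24 h means are 3395 and 127.

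*Protocol*

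**What the plan says.** Protocol section 1.2.1.4 ends with the NOAELs to be carried into the human dose calculation. Under "TOX 4 week (28 day) and corresponding exposure levels" it gives, for each species, a steady-state Cmax and a figure labelled AUCss(0-24):

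- Rat, 60 mg/kg b.i.d.: Cmax 193 µg/mL, AUC 2275 h*µg/mL.
- Dog, 20 mg/kg b.i.d.: Cmax 18.00 µg/mL, AUC 81.75 h*µg/mL.

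The source data are in section 1.2.1.3: "Table 5: Toxicokinetic parameters in plasma following a single and multiple oral administration in rats at different doses" and "Table 6: Toxicokinetic parameters in plasma following a single and multiple oral administration in dogs at different doses". Each table splits the day into AUC0-8 and AUC8-24 and also reports AUClast. For the rat, the text puts tlast at 24 h, "as this was the time point on which the last blood sample was taken". For the dog it says "For all groups t_{last} was 24h". On the timing of the second rat dose it says that "after the second dosing the peak plasma concentration was reached 4h after dosing, i.e. 12h".

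Animal exposure enters the escalation decision in section 3.3.3.2. There, human PK results from the previous dose level are used "in order to re-estimate the safety margin based on the animal-human exposure ratio", and that re-estimate has to be weighed before moving to the next dose.

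**The concern.** The two AUCs do not match the 24-hour values in the protocol's own tables, although the label says 0-24 h. They are the only exposures the protocol labels as NOAEL exposures, which makes them the natural numerator for the exposure ratio in section 3.3.3.2. A reader who takes the label at face value would divide a 16-hour animal AUC by a 24-hour human AUC. The resulting margin would be too small. Section 3.3.3.2 allows an intermediate dose, a repeated dose or a stop, so an understated margin could push towards one of those without cause.

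**Working it through.** **Inputs.** Week 4 values at the NOAEL dose, male and female, from Table 5 (rat, Group 3, 60 mg/kg b.i.d.) and Table 6 (dog, 20 mg/kg b.i.d.), in h*µg/mL:

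| | Rat M | Rat F | Dog M | Dog F |
|---|---|---|---|---|
| AUC0-8 | 1040 | 1200 | 41.0 | 50.1 |
| AUC8-24 | 1960 | 2590 | 77.2 | 86.3 |
| AUClast | 3000 | 3790 | 118 | 136 |

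**Step 1: reproduce the printed figures.** Mean of the male and female AUC8-24:

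- Rat: (1960 + 2590)/2 = 2275, as printed.
- Dog: (77.2 + 86.3)/2 = 81.75, as printed.

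**Step 2: rule out the other rows.** Male/female means of the remaining AUC rows at the same dose:

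| | Rat | Dog |
|---|---|---|
| Day 1 AUC0-8 | 931.5 | 50.35 |
| Day 1 AUC8-24 | 2155 | 94.95 |
| Day 1 AUClast | 3090 | 145.5 |
| Day 1 AUCinf | 4345 | 147.5 |
| Week 4 AUC0-8 | 1120 | 45.55 |
| Week 4 AUClast | 3395 | 127 |

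None gives 2275 or 81.75. Doubling the Week 4 AUC0-8 gives 2240 and 91.1, which also fails.

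**Step 3: what the 8-24 h window covers.** The second rat peak came 4 h after dosing, at 12 h, so the second dose was given at 8 h. In the dog, peaks came 1 or 2 h after dosing and the second peak was at 9 to 10 h, which again puts the second dose at 8 h. AUC8-24 is therefore the 16 hours from the second dose onward. The 0-8 h interval after the first daily dose is left out.

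**Step 4: the 0-24 h values.** With tlast at 24 h, AUClast is AUC0-24:

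- Rat: (3000 + 3790)/2 = 3395. The parts add up: 1040 + 1960 = 3000 and 1200 + 2590 = 3790.
- Dog: (118 + 136)/2 = 127. The parts give 41.0 + 77.2 = 118.2 and 50.1 + 86.3 = 136.4, which agree with the table after rounding.

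**Step 5: size.**

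- Rat: 2275/3395 = 0.670; inverse 1.49.
- Dog: 81.75/127 = 0.644; inverse 1.55.

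The protocol sets no minimum acceptable ratio. As an illustration, these are the animal-human ratios at human AUCs equal to the limits in section 3.5.4:

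| Human AUC (h*µg/mL) | Rat, 2275 | Rat, 3395 | Dog, 81.75 | Dog, 127 |
|---|---|---|---|---|
| 600 | 3.79 | 5.66 | 0.136 | 0.212 |
| 800 | 2.84 | 4.24 | 0.102 | 0.159 |
| 1000 | 2.28 | 3.40 | 0.082 | 0.127 |

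No ratio crosses 1. The limits stay below the rat NOAEL exposure and above the dog NOAEL exposure on either set of values.

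**Side check on Cmax.** The printed rat Cmax of 193 is the second-dose mean, (164 + 222)/2 = 193; the first-dose mean is (180 + 210)/2 = 195. This fits a summary line taken from the second-dose window. The dog value does not discriminate: (19.2 + 16.7)/2 = 17.95 for the second dose and (18.8 + 17.4)/2 = 18.1 for the first, against 18.00 printed. The effect on Cmax is about 1% and needs no action.

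**The case against.** The strongest reply is that nothing in the documents is shown to depend on these two numbers. The starting dose and the margins in Tables 8 and 9 come from body-surface conversion of the dose in mg/kg. The AUC limits in sections 3.3.3.2 and 3.5.4 are absolute, and the protocol does not say how they were derived. Section 3.3.3.2 does not name the species, the NOAEL, the AUC window or section 1.2.1.4 as its source, and the correct AUClast values are in Tables 5 and 6 for anyone who looks. The averaging itself is right, so this is a wrong row or a wrong label. The error also runs in the safe direction.

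All of that stands, and it limits the point to a minor one. It does not remove it. The label contradicts the protocol's own tables in both species, and section 3.3.3.2 makes an animal-human exposure ratio part of every escalation decision. Relabelling the figures as AUC8-24 would make the line true, but it would leave no 24-hour NOAEL exposure to set against a human 24-hour AUC.

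**Conclusion.** The concern holds. The figures labelled AUCss(0-24) in section 1.2.1.4 are Week 4 AUC8-24 means. The 0-24 h means are 3395 (rat) and 127 (dog) h*µg/mL, so an AUC margin built on the printed values is understated 1.49-fold and 1.55-fold. This rests on two readings of section 1.2.1.3: AUClast equals AUC0-24 because tlast was 24 h in all groups, and the summary values are simple male/female means, which the exact match in both species supports. The consequence for escalation is conditional on the printed values being used in section 3.3.3.2; the documents do not show that any decision was affected. Severity is minor and the direction is conservative.

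**What to change.** In section 1.2.1.4, replace 2275 with 3395 and 81.75 with 127, keep the 0-24 h label, and state in section 3.3.3.2 that these values are the reference for the animal-human AUC ratio. The cost is two corrected numbers and one cross-reference, with no new samples and no changed limits.

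A related but separate clarification could go into the substantial amendment already required before Part B. The stopping rule in section 3.5.4 that begins "In MAD part the mean at the steady state" takes the AUC over the dosing interval as its input but states the limit as AUC(0-24h), while section 6.1 defines AUC0-24 for the SAD part only. One sentence would settle it: at steady state, compare twice the 12-hour interval AUC with the AUC(0-24h) limits. This assumes that the two 12-hour intervals have equal exposure. The correction above does not depend on it.
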